10.1.2 Adverse Event Incidence

Administration of BMS-986165 12 mg BID to 37 subjects provides a 98% probability of observing at least 1 occurrence of any AE that occurs with 10% incidence in the population from which the sample is drawn. However, if the incidence rate is 6%, the probability of observing at least 1 occurrence of that AE with a sample size of 37 subjects is 90%.

[REDACTED]

[REDACTED]

[REDACTED]

[REDACTED]

[REDACTED]

[REDACTED]

[REDACTED]

[REDACTED]

10.2 Populations for Analyses

For purposes of analysis, the following populations are defined in Table 16.

Table 16: Analysis Populations

Population	Description
Enrolled Set	All subjects who sign the ICF.
Full Analysis Set (FAS)	All subjects who are randomized to study treatment; subjects will be grouped according to the treatment to which they are randomized within the IRT. The FAS population is the primary efficacy analysis population.
Safety Analysis Set	All randomized subjects who receive at least 1 dose of double-blind study treatment. Subjects will be analyzed according to treatment received.
[REDACTED]	

ICF = informed consent form; IRT = interactive response technology; [REDACTED]

10.3 Endpoints

Study endpoints are defined in [Section 4](#).

10.4 Statistical Analyses

The SAP will be developed and finalized before the database lock for the primary analysis or interim analysis (if applicable) and will describe the selection of subjects to be included in the analyses, and procedures for accounting for missing, unused, and spurious data.

Categorical data will be summarized as frequency counts and percentages. Continuous data will be summarized using n, mean, SD, median, minimum, and maximum unless otherwise specified.

During the treatment period, data will be presented for the following treatments:

- BMS-986165 12 mg BID
- BMS-986165 6 mg BID
- Placebo

10.4.1 Efficacy Analyses

Efficacy data will be summarized using the FAS population unless otherwise stated. Variables will be summarized for all visits in which the variable is assessed. Efficacy data will be listed by treatment group. Baseline values are defined as the last nonmissing value prior to the first dose of study drug unless otherwise indicated.

10.4.1.1 Primary Endpoint

Analysis Method:

The proportion of subjects achieving clinical response at Week 12 and the associated 95% CI for the BMS-986165 12 mg BID treatment arm will be estimated using the Clopper-Pearson exact method. Supportive analysis using logistic regression for the clinical response (binary endpoint) may be performed, and the odds ratio between treatment groups and the corresponding 95% CI may be provided if the data are sufficient to do so.

Imputation Method:

Occurrence of intercurrent events may have an impact on the estimand of interest for the following types of subjects: (1) subjects who discontinue treatment or study early (ie, prior to Week 12); (2) subjects who start a protocol prohibited medication/therapy; or (3) subjects who are lost to follow-up or have otherwise missing endpoint data at or prior to the Week 12 assessment. In these cases, the primary endpoint will be determined using the “Composite Strategy” as defined in the International Council for Harmonisation (ICH) E9 (R1) addendum and will be considered a measure of nonresponse to treatment.⁵⁸ Subjects with the identified intercurrent event(s) will have their clinical response endpoint imputed as being a “nonresponder.” This is commonly known as nonresponder imputation.

Sensitivity analyses using different imputation methods may be performed and will be defined in the SAP.

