Subjects will receive and be trained on the electronic daily diary at the screening visit. Subjects are expected to complete this diary on a daily basis throughout their participation in the study. In order to confirm that subjects are successfully recording data in the electronic daily diary, sites should review subject compliance with completion of the electronic daily diary, as indicated in the Schedule of Activities ([Section 2](#)), or more frequently if required. For the purpose of eligibility assessment and efficacy analysis, the **3 most recent (not necessarily consecutive), valid, electronic subject diary entries recorded from the 7 days prior to the day of a study visit (or up to the day before a subject starts bowel preparation for an endoscopy, if that visit includes an endoscopy)** will be used to calculate the SF and RB subscores (see [APPENDIX 9](#)). Electronic diary entries for SF and RB are considered valid when no medications for constipation, diarrhea, or bowel irregularity are reported (through E-diary) as taken that day. Review of electronic daily diary compliance during these previsit (or preendoscopy) periods is recommended. Subjects are not eligible to participate in this study if they are unable to complete study procedures, which includes daily completion of the electronic diary. The modified Mayo score calculated to determine eligibility will also be used as the baseline disease activity score.

Endoscopic evaluations and collection of colonic tissue biopsies will be performed during the screening period, at Weeks 12 and 52, at unscheduled visits (if clinically indicated), and at early termination (ET) visits that occur at least 4 weeks after the last per protocol-required endoscopy in the double-blind period and any time after Week 20 in the OLE period. Endoscopy is encouraged in subjects terminating in the OLE period between Week 12 and Week 20. Endoscopic procedures will be video recorded and scored for disease activity by a blinded central reader. Histologic scoring of gastrointestinal tissue specimens will also be performed by a blinded central reader.

[figure not shown]

Subjects who meet the criteria for treatment failure will permanently discontinue IP and enter the posttreatment follow-up period ([Section 5.1.3](#)).

An independent Data Monitoring Committee (DMC) will be instituted to assess safety data ([Section 5.1.6](#)).

The study design schematic is presented in [Figure 1](#).

Figure 1: Study Design Schematic

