7.4 Dosage Modification

There is no provision for dose modification of study treatment.

Dose stabilization criteria for permitted UC treatments are detailed in Section 0 ([Table 8](#)). Modification of permitted UC treatments or dose regimens is allowed for safety reasons, or if a

subject experiences an AE attributable to that treatment. Subjects should continue to take their assigned treatment even if their clinical condition worsens (ie, they experience a “flare”), unless any of the criteria in [Section 8.1](#) are met. If a subject’s clinical condition worsens before Week 12 of the treatment period to the extent that rescue therapy is required, based on the investigator’s judgment, the subject must discontinue study treatment (IP or placebo) in favor of appropriate alternative available treatment.

See [Section 8.1.1](#) for information regarding temporary interruption of study treatment.

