7.7 Concomitant Therapy

All medications taken from within 4 weeks before the first dose of study treatment until 30 days after the last dose of IP or last visit (whichever comes later) must be recorded on the appropriate eCRF.

Other than existing treatment for UC (with restrictions as described in the eligibility criteria [[Section 6](#)]), concomitant medications (prescription, over-the-counter [OTC], or herbal) should be

administered during the study only if they are prescribed for treatment of specific medical reasons separate from UC.

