7.7.3 Dose Stabilization Rules for Permitted UC Treatments

Use of concomitant oral 5-ASAs or oral corticosteroids [REDACTED] is permitted, subject to the dose stabilization rules outlined in Table 8. Probiotics are allowed with no restrictions on use. Subjects will continue their existing UC treatment(s) during the study, provided the treatment complies with the eligibility criteria (see [Section 6.1](#), [Section 6.2](#), and [Table 6](#)).

Dose reduction or discontinuation of 5-ASAs or corticosteroids is allowed during the study if this is required for subject safety reasons, such as if a subject experiences an AE attributable to those medications. The rationale for dose reduction or discontinuation must be documented in source documents. The AE or SAE eCRF must be completed, if applicable.

Table 8: Dose Stabilization Rules for Allowed Concomitant Medications

Medication/Formulation	Notes
5-ASAs (oral):	
 The oral 5-ASA regimen must be at a stable dose for at least 2 weeks prior to the initial screening visit (signing of ICF). Dose reduction (or discontinuation) is only allowed within this period for safety reasons, or if a subject experiences an AE attributable to the 5-ASA regimen.

Table 8: Dose Stabilization Rules for Allowed Concomitant Medications

Medication/Formulation	Notes
	
Stable doses are encouraged after randomization for the duration of the 12-week double-blind treatment period.
[REDACTED]	
[REDACTED] must be at a stable dose for at least 2 weeks prior to the initial screening visit (signing of ICF). Dose reduction (or discontinuation) is only allowed within this period for safety reasons or if the subject experiences an AE attributable to the [REDACTED]. This must be discussed with the BMS Medical Monitor/designee.After randomization, a stable dose is required for the duration of the 12-week treatment period. Dose reduction (or discontinuation) is only allowed within the treatment period for safety reasons, or if the subject experiences an AE attributable to the [REDACTED]. This must be discussed with the BMS Medical Monitor/designee.Throughout the study, an increase in [REDACTED] dose above the baseline dose is not permitted.
Probiotics:	
Probiotics are allowed. Dose stabilization is not required.

5-ASA = 5-aminosalicylic acid; AE = adverse event; ICF = informed consent form; [REDACTED]

[REDACTED]

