- Progestogen-only oral hormonal contraception, where inhibition of ovulation is not the primary mechanism of action (This method of contraception cannot be used by WOCBP participants in studies where hormonal contraception is prohibited.)

Unacceptable Methods of Contraception

- Periodic abstinence (calendar, symptothermal, postovulation methods)
- Withdrawal (coitus interruptus)
- Spermicide only
- LAM

COLLECTION OF PREGNANCY INFORMATION

Guidance for collection of Pregnancy Information and outcome of pregnancy on the Pregnancy Surveillance Form is provided in [Section 9.2.5](#) and [APPENDIX 3](#).

APPENDIX 5 CRITERIA TO DEFINE INADEQUATE RESPONSE (PRIMARY), LOSS OF RESPONSE (SECONDARY), AND INTOLERANCE TO PREVIOUS STANDARD OF CARE MEDICATION(S)

Inadequate response, loss of response, and/or intolerance to each standard of care UC treatment is defined as follows:

- Oral 5-aminosalicylic acids (5-ASAs) (eg, mesalamine, sulfasalazine, olsalazine, or balsalazide):
 - Signs and symptoms of persistently active disease despite a history of at least one 4-week regimen at highest dose (institutional practice)
 - Documented history of intolerance
- Corticosteroids (eg, prednisone [or equivalent] or budesonide [or equivalent]):
 - Signs and symptoms of persistently active disease despite a history of at least one 4-week induction regimen that included a dose equivalent to [REDACTED]
[REDACTED] OR
 - At least 2 failed attempts to [REDACTED] corticosteroids below a dose that is equivalent to oral prednisone 10 mg/day (or equivalent) or budesonide 3 mg/day (or equivalent) on 2 separate occasions (ie, steroid-dependent disease); OR
 - Documented history of intolerance of corticosteroids where subject developed adverse reactions including, but not limited to, Cushing's syndrome, osteopenia/osteoporosis, hyperglycemia, insomnia, cataracts, refractory steroid acne, or infection.
- Immunomodulators (eg, azathioprine [AZA], 6-mercaptopurine [6-MP], or methotrexate [MTX]):
 - Signs and symptoms of persistently active disease despite a history of at least one 8-week regimen of oral AZA, oral 6-MP, or oral or injectable MTX (per country's approved label); OR
 - History of intolerance of at least 1 immunomodulator (eg, nausea/vomiting, abdominal pain, pancreatitis, liver function test abnormalities, lymphopenia).
- Anti-tumor necrosis factor (TNF) agents (eg, infliximab, adalimumab, or golimumab):

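### Does the nonresponder rule for the primary endpoint miss subjects whose permitted UC background therapy is raised before Week 12?

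*Combined protocol and SAP*

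**What the plan says.** Section 10.4.1.1 uses a composite strategy with three nonresponder events. The first is discontinuing treatment or study before Week 12. The second is "2) subjects who start a protocol prohibited medication/therapy". The third is loss to follow-up or otherwise missing endpoint data. Clinical response itself (Section 9.1.2, Table 10) is defined by modified Mayo changes only and carries no condition on background therapy.

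Oral 5-ASAs and oral corticosteroids are permitted background drugs (Section 7.7.3) and are not among the visible rows of the prohibited list (Table 6). For 5-ASA, Table 8 says "Stable doses are encouraged after randomization for the duration of the 12-week double-blind treatment period". For a second Table 8 drug, whose name is blacked out, a "dose above the baseline dose is not permitted" at any time in the study.

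Section 7.4 says "Modification of permitted UC treatments or dose regimens is allowed for safety reasons" or for an adverse event attributable to the drug. If worsening before Week 12 requires rescue, "the subject must discontinue study treatment (IP or placebo) in favor of appropriate alternative available treatment". Section 5.1 adds: "Subjects who meet the criteria for treatment failure will permanently discontinue IP".

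**The concern.** Read literally, the second event is triggered by starting something prohibited. Raising the dose of a drug the subject already takes, and is allowed to take, is neither a start nor, on its face, prohibited. For 5-ASA the protocol only encourages a stable dose after randomization. A subject could therefore increase 5-ASA in Week 6, stay on study drug, supply complete Week 12 data and be counted as a responder.

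The primary estimate is a one-sample response rate in the 12 mg arm. Section 10.1.1 sets the expected interval beside an external placebo rate of 33%. In a one-sample estimate no concurrent arm offsets a contribution from added background therapy, so any such contribution would raise the rate directly. A rule left unwritten might also be settled after the data are known.

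**Working it through.** **Which increases are already nonresponse**

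| Situation before Week 12 | Visible provision | Counted as |
|---|---|---|
| Worsening that needs rescue | Section 7.4: study treatment stops | Nonresponse, event 1 |
| Treatment failure | Section 5.1: study drug stops permanently | Nonresponse, event 1 |
| Increase of the Table 8 drug with the blacked-out name | Table 8 forbids it; Section 8.1 requires discontinuation for failure to comply with the protocol | Nonresponse through event 1; also open to reading as prohibited therapy, event 2 |
| New drug given for UC | Section 7.7: apart from existing UC treatment, other medication is for reasons separate from UC | Outside the protocol; event 2 if prohibited, event 1 if it is rescue or leads to discontinuation |
| 5-ASA increase, none of the above, subject stays on study drug | Table 8 only encourages stability | Not assigned in the visible text |

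Only the last row is open. For it to change the result, a 12 mg subject must be taking 5-ASA, raise it above baseline before Week 12, not be classed as rescue, failure or non-compliance, remain on study drug with complete Week 12 data, and still meet the response criteria.

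**Reproducing the plan's interval**

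Inputs: n = 37 in the 12 mg arm (Section 10.1), and an expected response of about 60% with a Clopper-Pearson 95% interval of 42% to 75% (Section 10.1.1). Since 0.60 × 37 = 22.2, take x = 22.

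Lower limit = Beta quantile at 0.025 with parameters (x, n − x + 1). Upper limit = Beta quantile at 0.975 with parameters (x + 1, n − x).

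For x = 22: 22/37 = 59.5%, interval 42.1% to 75.2%. This matches the plan.

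**Effect of reclassifying k responders**

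Each one moves the estimate by 1/37 = 2.7 points. The values of k are assumptions; the documents give neither 5-ASA use nor an escalation rate.

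| k | Responders | Rate | 95% interval |
|---|---|---|---|
| 0 | 22/37 | 59.5% | 42.1% to 75.2% |
| 1 | 21/37 | 56.8% | 39.5% to 72.9% |
| 2 | 20/37 | 54.1% | 36.9% to 70.5% |
| 3 | 19/37 | 51.4% | 34.4% to 68.1% |
| 4 | 18/37 | 48.6% | 31.9% to 65.6% |

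The lower limit stays above 33% up to k = 3 and falls below it at k = 4. It falls just under 37%, the upper limit of the external placebo interval, at k = 2. Neither crossing decides anything formally: the synopsis says the sample size was chosen for precision, not power, and excluding 33% is a planning expectation, not a success rule.

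**Plausible size of k**

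Subjects who qualified through inadequate response to 5-ASA had "Signs and symptoms of persistently active disease despite a history of at least one 4-week regimen at highest dose (institutional practice" (Appendix 5), which limits their room to escalate. A subject whose dose is raised for worsening disease is also less likely to be a Week 12 responder, so not every escalation would be a reclassification.

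**The case for a change.** The best argument for a change is that the boundary is soft. Section 7.4 leaves the need for rescue to the investigator's judgment, so the same 5-ASA increase could be called rescue in one subject, giving nonresponse, and an adjustment in another, leaving response possible. The non-compliance criterion in Section 8.1 does not name dose increases and hardly reaches a 5-ASA increase when stability is only encouraged. Subjects can also qualify through other drugs or through intolerance, so prior highest-dose 5-ASA does not bring the count to zero. One sentence would settle it, using data already collected: Section 7.7 requires "All medications taken from within 4 weeks before the first dose of study treatment until 30 days after the last dose of IP" or the last visit, whichever is later, to be recorded.

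Part of this stands. No visible sentence assigns the 5-ASA case, and the grounds for modification in Section 7.4 are not cross-referred to the softer wording in Table 8.

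Three things keep it from being a defect. First, the places where such an increase would naturally be assigned, the treatment-failure criteria in Section 5.1.5 and the text after Table 8, are blacked out in the public copy, so an omission cannot be inferred. Second, Section 10.4 has the SAP finalized before database lock for the primary or any interim analysis, and Section 10.4.4 requires SAP text on any interim analysis before unblinding. That answers most of the worry about a choice made after the data are seen. Third, counting every 5-ASA increase as failure is not self-evidently right. Where the protocol merely encourages a stable dose, treating modest variation as part of background care is also a coherent estimand.

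**Conclusion.** The concern does not call for a change. It is a gap in the visible detail that analysts would be expected to fill when the SAP is finalized, and no wrong result from following the plan has been shown. Most routes by which added UC therapy could inflate the response rate already lead to nonresponse. The remainder is a narrow 5-ASA case of undocumented frequency.

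Its size is 2.7 points per reclassified responder. From 22 of 37, up to three reclassifications leave the interval above 33%, and four do not. This rests on 37 subjects in the 12 mg arm, 22 responders at the planned rate, and an assumed range of 0 to 4 affected responders. The conclusion also depends on ordinary practice: that the SAP says how 5-ASA increases are counted, in line with whatever Section 5.1.5 provides.

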10.4.1.2 Exploratory Endpoints

Statistical analyses of exploratory endpoints will be described in the SAP and finalized before database lock.

10.4.2 Safety Analyses

Safety endpoint analyses will be descriptive in nature. Safety data for each period will be summarized separately and combined. All safety data will be listed by treatment group.

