4 OBJECTIVES AND ENDPOINTS

Study objectives and specific endpoints are listed in [Table 3](#). Additional endpoints and analyses will be described in the statistical analysis plan (SAP), the Endoscopy Image Review Charter [REDACTED]. Selected efficacy endpoints are further defined in [Table 10](#).

Table 3: Study Objectives and Endpoints

Objective	Endpoints
Primary - Efficacy	

To estimate the efficacy of BMS-986165 at Week 12	
Proportion of subjects in clinical response at Week 12
Safety	

To assess the safety and tolerability of BMS-986165	
Number and proportion of subjects experiencing AEs, SAEs, AEs leading to discontinuation from the study, and AEIs throughout the study
Exploratory - Efficacy	
[REDACTED]	

Table 3: Study Objectives and Endpoints

Objective	Endpoints

 To explore the efficacy of BMS-986165 at Week 52 	
 Proportion of subjects in clinical remission at Week 52 Proportion of subjects in clinical response at Week 52 Proportion of subjects in endoscopic remission at Week 52 Proportion of subjects with endoscopic improvement at Week 52 Proportion of subjects with histologic improvement at Week 52 Proportion of subjects with corticosteroid-free remission at Week 52 Proportion of subjects in durable clinical response at Week 52 Proportion of subjects in durable endoscopic response at Week 52 Proportion of subjects in clinical response at Week 12
Exploratory	

 To explore the effect of BMS-986165 on PB immune cells 	
 Change from baseline in PB immune cells over time

 To explore the effect of BMS-986165 on the transcriptome in blood and colon biopsies 	
 Change from baseline in gene expression over time
Exploratory	
Exploratory - Health-related Quality of Life and Medical Resource Utilization	

 To explore the effect of BMS-986165 on PROs and quality of life 	
 Change from baseline at various time points for the IBDQ

Table 3: Study Objectives and Endpoints

Objective	Endpoints

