5.1.3 Open-label Extension Period

Subjects who are likely to derive a clinical benefit from ongoing participation in the study following Week 12, as judged by the investigator, are eligible to enter the OLE period. The OLE

period will last up to 40 weeks, to Week 52. Subjects will receive BMS-986165 6 mg BID PO during the OLE. There is no provision for dose escalation of IP during the OLE.

[REDACTED]

[REDACTED]

[REDACTED]

The symptomatic Mayo score at the Week 20 visit will be calculated using the **3 most recent (not necessarily consecutive) valid electronic subject diary entries recorded from the 7 days prior to the day of the study visit.**

[REDACTED]

Subjects who require any rescue therapy during the OLE period (Section 5.1.5) must permanently discontinue from study treatment (Section 8.1).

Endoscopy for the assessment of efficacy at Week 52 must occur in a window of 7 days prior to the Week 52 visit.

Endoscopy is required at the ET visit for subjects who permanently discontinue study treatment between Week 20 and prior to Week 52. Endoscopy is optional, but encouraged, for subjects who have an ET visit between Weeks 12 and 20.

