10.4.2.1 Adverse Events

Treatment-emergent AEs (TEAEs) are defined as AEs that occur after the subject received first dose of study treatment or if a preexisting condition worsens in severity or becomes serious after receiving the first dose of study treatment up to 30 days after the last dose of study treatment. All reported TEAEs, SAEs, deaths, AEs leading to study treatment discontinuation, and target AEs will be summarized by the Medical Dictionary for Regulatory Activities (MedDRA) SOC and PT.

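### The combined-period safety summary should report exposure-adjusted incidence by treatment at onset, because crude percentages in double-blind columns would count events that start on open-label 6 mg BID under placebo or 12 mg

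*Combined protocol and SAP*

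**What the plan says.** Section 10.4.2 (Safety Analyses) states that "Safety data for each period will be summarized separately and combined". It adds that "All safety data will be listed by treatment group" and calls the safety analyses descriptive. The only safety endpoint in Table 3 (Section 4) is "Number and proportion of subjects experiencing AEs, SAEs, AEs leading to discontinuation from the study, and AEIs throughout the study".

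Table 16 (Section 10.2) defines the Safety Analysis Set and its grouping in two sentences: "All randomized subjects who receive at least 1 dose of double-blind study treatment. Subjects will be analyzed according to treatment received". Section 10.4 names three presentation groups for the treatment period (12 mg BID, 6 mg BID and placebo) and sets the general statistic: "Categorical data will be summarized as frequency counts and percentages". It does not say where a subject who starts on 12 mg or placebo and moves to 6 mg belongs in a combined table.

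That move applies to every OLE entrant from those two arms. Section 5.1.3 says "Subjects will receive BMS-986165 6 mg BID PO during the OLE", for up to 40 weeks after 12 double-blind weeks. OLE subjects who need rescue therapy "must permanently discontinue from study treatment", so 40 weeks is an upper limit.

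Section 10.4.2.1 runs the treatment-emergent window from first dose "up to 30 days after the last dose of study treatment". It does not attribute events to a dose. No person-time rate appears in the supplied text.

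**The concern.** About 50 subjects (37 on 12 mg, 13 on placebo) could each contribute time on two treatments to the combined summary. There are two ways to form its columns, and with crude percentages neither gives a table that can be read by treatment.

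- **By double-blind treatment**, the natural reading of Table 16. Each subject has one column, but the placebo column takes in events that began on active drug, and the 12 mg column takes in events that began on 6 mg.
- **By treatment at onset.** Events are attributed correctly, but 6 mg is observed for a different length of time than 12 mg and placebo. A crude percentage grows with time at risk, so 6 mg can look better or worse for that reason alone.

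At stake is the readability of one planned table and of the whole-study proportion in Table 3. Section 5.1.6 describes this study as the first use in ulcerative colitis of doses above 6 mg BID. Section 3.2 says its safety data may inform Phase 3 dose selection.

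**Working it through.** **The plan's own safety figure.** Section 10.1.2 gives a 98% chance of seeing at least one event among 37 subjects at 10% incidence, and 90% at 6%. Check: 1 − 0.90^37 = 0.980 and 1 − 0.94^37 = 0.899. Both reproduce. They concern detection on 12 mg and do not bear on the combined table, for which the plan gives no figure.

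**Inputs from the documents.** Double-blind period 12 weeks; OLE up to 40 weeks, all on 6 mg BID; about 37 subjects on 12 mg and 13 on placebo.

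**Assumed inputs.** The documents give no adverse event rate, OLE entry share or mean OLE duration. Let p be the share entering the OLE, m the OLE weeks (the same for all entrants) and r the 12-week risk of a first event. The hazard is constant and equal for everyone, so there is no true dose effect.

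**Step 1. Share of a column's follow-up on open-label 6 mg**, columns by double-blind treatment: pm / (12 + pm).

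| OLE weeks | p = 50% | p = 100% |
|---|---|---|
| 8 | 4/16 = 25.0% | 8/20 = 40.0% |
| 20 | 10/22 = 45.5% | 20/32 = 62.5% |
| 40 | 20/32 = 62.5% | 40/52 = 76.9% |

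**Step 2. Effect on the placebo column.** Added percentage = p × [(1 − (1 − r)^((12+m)/12)) − r]. With r = 10% and p = 80%:

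- m = 8: 0.8 × (0.161 − 0.100) = 4.9 points; the column reads 14.9% instead of 10.0%; 0.6 of 13 subjects.
- m = 20: 0.8 × (0.245 − 0.100) = 11.6 points; 21.6%; 1.5 of 13.
- m = 40: 0.8 × (0.367 − 0.100) = 21.3 points; 31.3%; 2.8 of 13.

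These subjects count as placebo events only because of an event that began on 6 mg. At m = 20, r from 5% to 20% gives 0.8 to 2.6 of 13.

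**Step 3. Unequal OLE entry.** Entry depends on the investigator's judgement of likely benefit, so it may differ by arm. If 80% of the 12 mg arm and 40% of the placebo arm entered for 40 weeks at r = 10%, the crude combined risks would be 0.2 × 10% + 0.8 × 36.7% = 31% and 0.6 × 10% + 0.4 × 36.7% = 21%. The gap comes from follow-up time alone.

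**Step 4. Columns by treatment at onset, crude percentages.** Apparent ratio of 6 mg to 12 mg or placebo = [1 − (1 − r)^(m/12)] / r, where the true ratio is 1.

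| OLE weeks | r = 5% | r = 10% | r = 20% |
|---|---|---|---|
| 8 | 0.67 | 0.68 | 0.69 |
| 20 | 1.64 | 1.61 | 1.55 |
| 40 | 3.14 | 2.96 | 2.62 |

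At m = 12 the ratio is 1.0, because the observation times are then equal.

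**Step 5. Exposure-adjusted rate.** −ln(1 − r)/12 × 52.18 × 100. At r = 10% this is 45.8 per 100 patient-years in every column, whatever m and p are, so both distortions disappear under the constant-hazard assumption.

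**The case against.** The strongest reply is that the plan already protects the comparison that matters. The double-blind summary sets 12 mg against placebo over equal planned time, and in the OLE summary everyone takes 6 mg. The safety analyses are descriptive, no stated decision uses the combined table, and Table 3 does not ask for a comparison by dose. All of this stands and keeps the point small. It does not rescue the combined table, because a placebo column that holds events begun on active drug misleads even as description.

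It could also be said that table detail belongs in the SAP. Section 4 sends additional analyses there, and Section 10.4 leaves it the selection of subjects. No separate SAP is in the supplied text, so the rule may yet be set there. Section 10.4.2 itself does not defer the matter.

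A reader might infer two stronger things that the documents do not support:

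- **That subjects who change treatment have no column at all.** The Safety Analysis Set is defined by double-blind dosing, so treatment received most naturally means double-blind treatment, and Section 10.4 lists three groups. A column exists; the trouble is what it would contain.
- **That the 30-day window makes events just after Week 12 ambiguous and so touches the double-blind summary.** The window runs from the last dose of study treatment. Section 7 defines study treatment to cover all assigned investigational treatment, Section 8.1.1 speaks of a 52-week treatment period, and Table 1 (footnote o) has OLE supply dispensed at Week 12. For an OLE entrant the tail therefore follows the last OLE dose.

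**Conclusion.** The point holds as a cheap improvement, limited to the combined-period summary in Section 10.4.2 and the whole-study proportion in Table 3. Read naturally, the plan gives a combined table in which a quarter to three quarters of the follow-up under placebo and 12 mg may be on open-label 6 mg: 25% at 50% entry and 8 OLE weeks, 76.9% at full entry and 40 weeks. The exposure shares rest on assumed OLE entry and duration. The event figures also rest on an assumed risk and a constant common hazard. Under the alternative grouping even the direction of the distortion depends on OLE duration: the apparent ratio runs from 0.67 to 3.14 over the ranges shown. The documents do not show that the double-blind comparison of 12 mg with placebo, or the OLE summary, is compromised.

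**What to change.** In Section 10.4.2, or the SAP section that implements it, state for the combined summary that:

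1. each treatment-emergent event is attributed to the treatment being taken at onset;
2. exposure-adjusted incidence per 100 patient-years is reported by that treatment beside the crude counts;
3. no event that starts on OLE treatment is counted as placebo.

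The cost is a few sentences and a few extra tables from dosing and onset dates, with no new data. There are two drawbacks. The rates assume a roughly constant hazard. Placebo rates will also be imprecise: 13 × 12 / 52.18 = about 3.0 patient-years if all 13 complete 12 weeks, so one event gives 33 per 100 patient-years with an exact Poisson 95% CI of 0.8 to 186. That is why the crude counts should stay beside the rates.
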